4.2.8.1 Definition

The randomised period is defined in Section 3.3.2.2 and target PN in Section 4.2.1.2.

4.2.8.2 Derivations

The absolute change and percentage change from baseline in target PN volume at each assessment will be calculated. For each assessment, two target PN volumes will be available from two independent radiologists. The average of the two target baseline PN volumes and the average of each post-baseline target PN volume will be used to calculate the absolute change and percentage change from baseline. The best change in volume is the largest decrease from baseline or the smallest increase from baseline in the absence of a reduction and will include all on-treatment MRI volumetric assessments (see Section 3.3.2) during the randomised period prior to the earliest of death in the absence of progression, any evidence of progression, or the last evaluable REiNS assessment if the patient has not died or progressed.

The best percentage change from baseline in target PN volume will be derived using the best evaluable while on-treatment MRI volumetric assessment (see Section 3.3.2.1) during the randomised period.

4.2.8.3 Intercurrent Events

Follow the same approach as outlined for the primary endpoint in Section 4.2.1.7

4.2.8.4 Primary Analysis of Best Percentage Change From Baseline in Target PN Volume During the Randomised Period

The effect of selumetinib on best percentage change from baseline in target PN volume during the randomised period will be estimated from an analysis of covariance (ANCOVA) model including covariates for baseline target PN volume, baseline PAINS-pNF chronic target PN pain intensity group (<3, \geq 3), and geographical region. The number of patients,

unadjusted mean, and LS means for each treatment group should be presented together with the difference in LS means, 95% CI, and corresponding p-value.

Data will be summarised and analysed using FAS. Data collected during the randomised period (see Section 3.3.2.1) adhering to the intercurrent event strategy (refer to Section 4.2.8.3) are included.

4.2.8.5 Supplementary Analyses of Best Percentage Change From Baseline in Target PN Volume During the Randomised Period

Percentage change from baseline will be calculated based on all on-treatment MRI volumetric assessments without excluding scans during study intervention interruption. The analysis will follow the same methods as the primary analysis of percentage change from baseline during the randomised period. Data will be summarised and analysed using a subset of the FAS including patients with measurable target PN at baseline per ICR who received at least one dose of study intervention and had a least one post-baseline target PN volume during the randomised period.

The absolute values, change in target PN volume from baseline, and percentage change in target PN volume from baseline will be summarised using descriptive statistics and presented at each timepoint during the randomised period by treatment group.

Waterfall plots and histograms ([Mercier et al 2019](#)) will summarise the best percentage change from baseline in target PN volume.

For the waterfall plot, each patient's best percentage change in PN volume will be represented as a separate bar, with the bars ordered from the largest increase to the largest decrease.

For the histograms, each histogram bar will represent the number of patients within specific ranges of best percentage change in target PN size from baseline.

The waterfall plot and histograms will be summarised and analysed using a subset of the FAS including patients with measurable target PN at baseline per ICR who received at least one dose of study intervention and had at least one post-baseline target PN volume during the randomised period.

The analysis will be repeated using the same method but will not be restricted to the randomised period using the Selumetinib FAS.

4.2.9 Chronic Target PN Pain Palliation During the Randomised Period

4.2.9.1 Definition

Chronic target PN pain palliation at a cycle is defined as the occurrence of both of the following events:

- 1) Improvement of ≥ 2 in average PAINS-pNF chronic target PN pain intensity score
- 2) No increase in chronic PN pain medication compared to baseline for that cycle
 - i. Assuming that the patient had non-missing chronic PN pain medication data (see Section 4.2.9.4 for definition of “missing”) and did not meet the criteria of eDiary chronic PN pain medication score increase of ≥ 1 compared to baseline (primary definition; see Section 4.2.9.2).
 - ii. Assuming that the patient had non-missing chronic PN pain medication data (see Section 4.2.9.4 for definition of “missing”) and did not meet the criteria of eDiary chronic PN pain medication score increase of ≥ 0.5 compared to baseline (first sensitivity definition; see Section 4.2.9.2).
 - iii. Assuming that the patient had a non-missing investigator electronic case report form (eCRF) assessment (see Section 4.2.9.4 for definition of “missing”) and did not meet the criteria of “increased” due to “PN pain” compared to baseline (second sensitivity definition; see Section 4.2.9.2).

Table 14 summarises the chronic target PN pain definitions that will be examined.

Table 14: Definitions of Chronic Target PN Pain Palliation

Definition	Chronic target PN pain intensity threshold for palliation	Non-missing pain medication data and pain medication increase based on
Primary	2	eDiary chronic PN pain medication score increase of ≥ 1
Sensitivity 1	2	eDiary chronic PN pain medication score increase of ≥ 0.5
Sensitivity 2	2	Investigator’s assessment of “increased” “due to increased PN pain”
Sensitivity 3	From psychometric work*, if different than 2	eDiary chronic PN pain medication increase of ≥ 1
Sensitivity 4	From psychometric work*, if different than 2	eDiary on chronic PN pain medication score of ≥ 0.5
Sensitivity 5	From psychometric work*, if different than 2	Investigator’s assessment of “increased” “due to increased PN pain”

PN, plexiform neurofibroma.

*Psychometric validation of the PAINS-pNF instrument in this study will be performed based on blinded data before DCO1, and a clinically meaningful within-patient change will

be derived based on interim data. In case this value is different than 2, an additional definition of chronic target PN pain palliation will be an improvement of greater or equal than the clinically meaningful within-patient change derived from the psychometric analysis.

Pain palliation will be assessed in all post-baseline cycles during the randomised period in the Pain FAS.

The randomised period is defined in Section [3.3.2.2](#).

4.2.9.2 Derivations

Detailed derivations for PAINS-pNF chronic target PN pain intensity average cycle score is defined in Section [4.2.2.1.2](#).

An increase in eDiary-reported chronic PN pain medication per cycle compared to baseline is defined as one of the following:

Primary definition: Increase from baseline ≥ 1 point (increase to a stronger class of analgesic medication on the WHO modified analgesic ladder [see Section [3.3.8](#), Table 2]) with the same drug of the strongest score taken for at least 3 days in a 28-day cycle (refer to Section [3.3.8](#),

- [Figure 3](#)).
- Sensitivity definition 1: Increase from baseline ≥ 0.5 point (increase to a stronger class of medication on the WHO modified analgesic ladder [see [Section 3.3.8 Table 2](#)] or an increase in the daily dose or number of pain medications within the same analgesic class) with the same drug taken for at least 3 days in a 28-day cycle (refer to [Section 3.3.8](#),

- [Figure 3\)](#)
- Sensitivity definition 2: “No increase in PN pain medication at a specific cycle compared to baseline” will be identified as those patients who had available eCRF data on investigator assessment of analgesic requirement but did not have an investigator’s assessment of “increased” analgesic requirement “due to PN pain”.

Following the definitions in Section [4.2.9.1](#), chronic target PN pain palliation values will be 1 for patients experiencing pain palliation and 0 for patients that do not.

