DCO, data cut-off; FAS, full analysis set; ORR, objective response rate; PAINS-pNF, PAin INTensity Scale for Plexiform Neurofibroma; PlexiQOL, Plexiform Neurofibroma Quality of Life scale; PN, plexiform neurofibroma.

3.3.8 PN Pain Medication Modified WHO Analgesic Ladder and PN Pain Medication Score Changes

The eDiary PN pain medications reported daily by the patient will be assigned by medical review to a drug class and analgesic ladder score identified in [Table 2](#). In case a combination of one or more drug is reported in a daily diary entry, the strongest drug class and its related daily dose will be selected during the medical adjudication process. If all the medications of the combination belong to the same class, precedence will be given to a drug already taken by the patient. Otherwise, the first drug of the combination will be selected.

The strongest drug class and the highest analgesic ladder score at each cycle will be programmatically identified separately for both chronic PN medications and spike PN medications.

Table 2: Modified WHO Analgesic Ladder

Score	Drug class	Examples	
0	No Analgesia		
1	Non-opioids	Acetaminophen, NSAIDs	
2	Neuropathic/ other non-typical pain medications	Pregabalin, Gabapentin, Amitriptyline, Duloxetine Muscle relaxants	Additional class of pain medications added to include typical pain medications used by NF1-PN patients
3	Weak opioids	Codeine	
4	Strong opioids	Morphine	

[figure not shown]
NF1, neurofibromatosis type 1; NSAID, nonsteroidal anti-inflammatory drug; PN, plexiform neurofibroma; WHO, World Health Organisation.

For chronic PN pain medication, changes from baseline will be derived. This definition is used for the derivation of PRO endpoints such as decrease in PN pain medication and chronic target PN pain palliation, as well as the intercurrent event “increase in chronic PN pain medication” of the key secondary PAINS-pNF chronic target PN pain intensity estimand as described in Section 4.2.2.1. No changes from baseline are derived for the spike PN chronic medication.

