Following the identification of the strongest drug class in chronic PN pain medication at each cycle, the change in score at each cycle compared to baseline will be programmatically identified following the algorithm outlined in Figure 3. If changes in the strongest drug class from baseline do not follow under the categories of Figure 3. of “Increased” or “Decreased,” the category “No Change” will be assigned. For the cycles where no PN chronic medication has been recorded in the eDiary, the change will be set to “Missing”.

A secondary definition for change from baseline in PN pain medication (Increased/Decreased/No Change) is derived using the investigator analgesic requirement assessment recorded on the e-CRF, indicating whether the reason is PN pain or other pain.

Figure 3: PN Pain Medication Score Changes Algorithm

PN, plexiform neurofibroma; WHO, World Health Organisation.

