For the intercurrent event of increase in pain medication, the first date of increase in chronic pain medication meeting the minimum requirement for increase per section 3.3.8 will be identified. All daily PAINS-pNF scores on and after the first date of increase in pain medication will be set to missing for the cycle in which the increase in pain medication occurs. After setting these daily values to missing, if there is sufficient (i.e., meets the criteria of needing at least 4 daily scores in at least 3 non-overlapping 7-day periods in the 28-day cycle [per Section 4.2.2.1.2]) observed daily data prior to increase in medication to derive the cycle PAINS-pNF score, then these data will be used to derive the cycle score. This derived score will be used to overwrite the actual observed cycle score. Otherwise, the cycle score will be set to missing to be imputed under MNAR using reversion-to-baseline. This method will be repeated for each cycle in which an increase in pain medication occurs up to and including cycle 12. The resulting dataset from repeating this process can contain non-monotone missing data for 2 reasons: (i) missing score in cycle x due to an increase in pain medication (and a cycle score cannot be derived using daily data prior to the intercurrent event), but cycle score is not missing for cycle x+1 and; (ii) missing cycle score due to reasons not related to an increase in pain medication (e.g. subject's eDiary broke during the cycle).

MI methods can be summarised in three steps: imputation phase, analysis phase, and pooling phase.

- Imputation Phase

By means of the SAS procedure PROC MI, 25 copies (assuming 10% to 35% of missing data) of the original dataset will be simulated, where missing continuous endpoint values will be replaced with a 2-step imputation process.

By means of the MI SAS procedure PROC MI, 25 copies of the original dataset will be simulated with random seed = 54321, where missing endpoint values will be replaced with a 2-step imputation process.

The first step will be to impute non-monotone missing data (“holes” while on-treatment), which will be imputed under the MAR assumption by means of a multivariate joint Gaussian imputation model using the stochastic Markov Chain Monte Carlo (MCMC) method.

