4.2.11.4 Handling of Dropouts and Missing Data

For the chronic PN pain medication based on the eDiary, the strongest class of pain medications reported over the 28 days of each cycle will be based on observed scores, that is, days with missing information will be ignored in the derivation.

For purposes of the analysis of decrease in pain medication, 1) if the pain medication data provide sufficient evidence to rule out a decrease for a cycle (see Section 4.2.9.2), that cycle is considered not to have missing pain medication data; 2) if, due to missing *daily*

pain medication data as defined in Section 4.2.9.4, the cycle does not provide sufficient evidence to rule out either an increase or a decrease in pain medication for a cycle, that cycle will be considered to have missing pain medication data.

For the investigator's assessment of change in pain medication, analyses will be based on observed data.

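### As worded, the primary medication-increase rule lets one or two days of a stronger drug cancel a sustained analgesic step-up, so the cycle can count as pain palliation

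*SAP*

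**What the plan says.** SAP 3.3.8 scores each daily eDiary entry on a modified WHO ladder: 0 none, 1 non-opioid, 2 neuropathic or other, 3 weak opioid, 4 strong opioid. When a day's entry is a combination, "the strongest drug class and its related daily dose will be selected during the medical adjudication process".

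The cycle is then summarised: "The strongest drug class and the highest analgesic ladder score at each cycle will be programmatically identified separately", for chronic and spike medication. No minimum number of days is attached. SAP 4.2.11.4 points the same way: "the strongest class of pain medications reported over the 28 days of each cycle will be based on observed scores", with missing days ignored.

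The change from baseline comes second: "Following the identification of the strongest drug class in chronic PN pain medication at each cycle, the change in score at each cycle" is derived using Figure 3. If the change is neither an increase nor a decrease, "the category “No Change” will be assigned".

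SAP 4.2.9.2 gives the primary definition of an increase as "Increase from baseline ≥ 1 point (increase to a stronger class of analgesic medication on the WHO modified analgesic ladder", on the condition that this occurs "with the same drug of the strongest score taken for at least 3 days in a 28-day cycle". SAP 4.2.9.1 makes failure to meet that criterion one of the two conditions for palliation. The other is a pain improvement of at least 2.

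**The concern.** A 3-day minimum makes sense as a way to disregard isolated use. Here it is tied to the strongest score of the cycle, and a single day can set that score. A brief use of a stronger drug then moves the 3-day test onto that drug. The drug fails the test, and the visible text does not send the derivation back to the lower class that was used for weeks and is itself above baseline. More analgesia can turn an increase into no increase.

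The error runs towards response. A participant who escalated analgesia for most of a cycle and whose pain fell by at least 2 would be scored as palliated. Table 15 (SAP 4.2.9.3) gives medication change no other handling, because it is treated as part of the endpoint. Time to palliation (SAP 4.2.10) uses the first palliated cycle, so one such cycle can create an event or bring it forward.

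**Working it through.** The SAP states no figure that depends on this rule, so there is nothing to reproduce. The check applies the written rule to example cycles.

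**Inputs.** Ladder scores are from SAP Table 2. The cycle maximum has no day minimum (SAP 3.3.8 and 4.2.11.4). The 1-point threshold and the 3-day condition are from SAP 4.2.9.2. The example baseline score is b = 1 (non-opioid).

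**Rule as written.** Let M be the highest score on any day of the cycle. Let n be the largest number of days on any one drug with score M. The cycle is an increase only if M − b ≥ 1 and n ≥ 3.

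**Comparison rule.** Let M* be the highest score for which one drug was taken on at least 3 days. The cycle is an increase if M* − b ≥ 1.

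| 28-day cycle, b = 1 | M | n | As written | M* | Comparison |
|---|---|---|---|---|---|
| 28 d codeine | 3 | 28 | increase | 3 | increase |
| 27 d codeine + 1 d morphine | 4 | 1 | not increased | 3 | increase |
| 26 d codeine + 2 d morphine | 4 | 2 | not increased | 3 | increase |
| 25 d codeine + 3 d morphine | 4 | 3 | increase | 4 | increase |
| 26 d gabapentin + 2 d codeine | 3 | 2 | not increased | 2 | increase |
| 26 d acetaminophen + 2 d morphine | 4 | 2 | not increased | 1 | not increased |
| 25 d acetaminophen + 3 d codeine | 3 | 3 | increase | 3 | increase |

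Down the first four rows, the written rule goes from increase to not increased and back again as morphine days rise from 0 to 3. The sixth row shows that the comparison rule still disregards isolated 2-day use. The result is the same if codeine is also taken on the morphine days, because only the strongest class is kept for a day.

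**Who is exposed.** The cancellation needs two ladder classes above baseline: one held for at least 3 days and a higher one used for 1 or 2 days. The possible (held, higher) pairs are:
- b = 0: (1,2), (1,3), (1,4), (2,3), (2,4), (3,4)
- b = 1: (2,3), (2,4), (3,4)
- b = 2: (3,4)
- b = 3 or 4: none

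**From cycle to endpoint.** A cycle that is not increased scores 1 for palliation only if average pain also improved by at least 2 in that cycle. The misclassified cycles that matter are the subset meeting both conditions.

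**The case against.** The strongest objection is that the operative algorithm cannot be seen. SAP 3.3.8 and 4.2.9.2 both refer to Figure 3, which is missing from the available text; that absence is not a fault in the plan. The figure may already step down to the highest class meeting 3 days. The phrase in SAP 4.2.9.2 could also be read as the strongest score sustained for 3 days. This part of the objection stands: the defect is established for the wording, not for the program. The sentences in SAP 3.3.8 and 4.2.11.4 define strongest without a day minimum, so the written text favours the problematic reading and needs correcting even if the figure is sound.

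The objection that the reach is narrow also stands. Chronic and spike medications are scored separately, so a stronger drug logged only for spike pain does not enter. Palliation lies outside the multiple testing procedure. Sensitivity definition 1 omits the reference to the strongest score and, as worded, would catch the sustained step-up. Sensitivity definition 2 uses the investigator's assessment. These do not repair the primary definition. Sensitivity definition 1 also lowers the threshold to 0.5 points, so a difference from the primary result could not be traced to this rule alone.

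Three stronger readings are tempting but unsupported:
- **That every step-up cycle with brief stronger use is misclassified.** This would require Figure 3 to have no fallback. It also could not apply at baseline scores 3 or 4.
- **That two different strong opioids on 2 days each, with no other step-up, show the same fault.** That cycle fails because one drug must reach 3 days, which is a persistence requirement the sponsor may intend. No increase is cancelled there.
- **That the first key secondary result is distorted.** Its primary MMRM takes a treatment-policy approach to medication changes (Table 9). Its medication-increase sensitivity analysis works by date: "the first date of increase in chronic pain medication meeting the minimum requirement for increase per section 3.3.8 will be identified". The visible text of SAP 3.3.8 gives no such minimum, so whether codeine held for weeks would qualify on its own depends on Figure 3. An effect there is possible but not shown.

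**Conclusion.** The point holds for the text as written. For a participant with a baseline score of 0 to 2, a sustained step-up plus 1 or 2 days of a still stronger drug is classed as not increased, although the step-up alone is an increase. If pain also falls by at least 2, the cycle counts as palliation under the primary definition and in time to palliation.

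This rests on reading strongest at cycle level and on Figure 3 containing no fallback. The documents do not say how often such cycles occur or whether they would be more common in one arm, so neither the size nor the direction of any bias between arms can be given. No confirmatory test is affected. The reason to act is that a secondary responder definition gives a perverse result for a recognisable pattern of use, and correcting it is cheap.

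**What to change.** For the increase classification, define the cycle class as the highest ladder class for which one drug was taken on at least 3 days in the 28-day cycle. Call an increase when that class exceeds the baseline class. This keeps the same-drug requirement and still ignores isolated 1- or 2-day use. State that a cycle in which no drug reaches 3 days is not an increase.

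Check that Figure 3 does the same, and align SAP 3.3.8, 4.2.9.2 and 4.2.2.1.6.1, including an explicit statement in 3.3.8 of the minimum requirement that 4.2.2.1.6.1 relies on. The decrease classification also starts from the strongest class, so state whether the new cycle class applies there or only to increases.

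If Figure 3 already contains the fallback, only the wording changes. Otherwise there is also a small programming change. No new data are needed. The change should be made before treatment codes are available to those who write the derivation.

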4.2.9.3 Intercurrent Events

The intercurrent event strategy for the chronic target PN pain palliation is described in [Table 15](#).

Table 15: Intercurrent Event Strategy for Chronic Target PN Pain Palliation

Intercurrent event	Strategy	Details
Changes to patients’ chronic PN pain medication	N/A	Included in endpoint definition.
Randomised study intervention discontinuation	Hypothetical strategy	PAINS-pNF chronic target PN pain intensity scores following randomised study intervention discontinuation will not be collected and will be modelled through direct likelihood techniques.
Early crossover from placebo to selumetinib in patients with documented progression on imaging (as determined by ICR per REiNS criteria)	While on-treatment strategy	PAINS-pNF chronic target PN pain intensity scores and pain medication data after early crossover from placebo to selumetinib will be set to missing.
Prolonged study intervention interruption (defined as a study intervention interruption greater than or equal to 28 days)	While on-treatment strategy	The following rules will be followed to align with the while on-treatment strategy: 
- PAINS-pNF chronic target PN pain intensity scores and pain medication data during the first 28 days of prolonged treatment interruption will be included.- PAINS-pNF chronic target PN pain intensity scores and pain medication

		
after the first 28 days of prolonged treatment interruption will be excluded.
 
 - PAINS-pNF chronic target PN pain intensity scores and pain medication data from the day of study intervention recommencement will be included.
Target PN resection	Treatment policy strategy	PAINS-pNF chronic target PN pain intensity scores and pain medication data after a target PN surgical resection will be included in the analysis.

ICR, independent central review; N/A, not applicable; PAINS-pNF, PAin INtensity Scale for Plexiform Neurofibroma; PN, Plexiform Neurofibroma; REiNS, Response Evaluation in Neurofibromatosis and Schwannomatosis.

